## 3 OBJECTIVES AND ENDPOINTS

Objectives	Endpoints
Primary 

To assess the long-term use of LCM oral solution dosed at 2mg/kg/day to 12mg/kg/day when administered to pediatric study participants with epilepsy who have completed EP0034 or SP848

	

TEAEs reported by the study participant or caregiver or observed by the Investigator

Withdrawals from study due to TEAEs

Withdrawals from study due to SAEs

Modal daily dose (mg/kg/day)

Maximum daily dose (mg/kg/day)

LCM=lacosamide; SAE=serious adverse event; TEAE=treatment-emergent adverse event

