### **8.3.1 Time period and frequency for collecting AE and SAE information**

All AEs and SAEs will be collected from the signing of the ICF until the end of the study at the time points specified in the Schedule of Activities (Table 1-1).

In order to ensure complete safety data collection, all AEs occurring during the study (ie, after the signing of the ICF), including any pretreatment and posttreatment periods required by the protocol, must be reported in the eCRF even if no study medication was taken but specific study procedures were conducted. This includes all AEs not present prior to the Visit 1 and all AEs that recurred or worsened after Visit 1.

All SAEs will be recorded and reported to the Sponsor or designee within 24 hours, as indicated in Appendix 3. The Investigator will submit any updated SAE data to the Sponsor within 24 hours of it being available.

The Investigator is specifically requested to collect and report to UCB (or its representative) any SAEs (even if the Investigator is certain that they are in no way associated with the study medication), up to 30 days from the end of the study for each study participant, and to also inform study participants of the need to inform the Investigator of any SAE within this period. Serious AEs that the Investigator thinks may be associated with the study medication must be reported to UCB regardless of the time between the event and the end of the study.

The method of recording, evaluating, and assessing causality of AE and SAE and the procedures for completing and transmitting SAE reports is provided in Appendix 3.

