## **9.3        Planned safety analyses**

### **9.3.1      Safety analyses**

Treatment-emergent AEs will be defined as those events which started on or after the date of first dose of LCM in EP0151, or events for which severity worsened on or after the date of first dose of LCM in EP0151. Adverse events which occur within 30 days after final dose of LCM in EP0151 will be considered treatment-emergent.

Adverse events will be coded using the Medical Dictionary for Regulatory Activities® (MedDRA). Pretreatment AEs, TEAEs, non-serious TEAEs, withdrawals due to TEAEs, withdrawals due to SAEs, and SAEs will be tabulated by system organ class and preferred term. The incidence of TEAEs will also be summarized by intensity and by relationship to LCM. In addition, all AEs will be listed.

Long-term use of LCM will be assessed by modal daily dose (mg/kg/day) and maximum daily dose (mg/kg/day). These doses will be summarized using descriptive statistics, along with duration of exposure (days).

Actual measurements and changes from Baseline in vital signs, body weight, height, and calculated BMI will be summarized descriptively by visit. In addition, shift tables may be used to evaluate the number and percent of study participants having a different post-Baseline status when compared with their Baseline status.

The endpoints for assessment of long-term use include TEAEs, study participant withdrawals due to TEAEs and SAEs, modal daily dose, and maximum daily dose. Available data related to these measurements will be presented in participant data listings.

Responses to the C-SSRS will be presented in participant data listings.

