5.3.1 Definition of endpoints

TEAEs reported by the study participant or caregiver or observed by the Investigator

TEAEs will be defined as those events which started on or after the date of first dose of LCM in EP0151, or events for which severity worsened on or after the date of first dose of LCM in EP0151. AEs which occur within 30 days after final dose of LCM in EP0151 will be considered treatment-emergent.

Withdrawals from study due to TEAEs

Primary reason for premature study termination is collected in eCRF, one of which is AE. Together with the AE information for such participants collected in eCRF, early termination due to TEAE will be derived based on the definition of TEAE.

Withdrawals from study due to SAEs

The premature study termination due to AE collected in eCRF will be further considered for AEs indicated as serious in the eCRF.

Modal daily dose (mg/kg/day)

Definition of modal daily dose is in Section [5.1.2.4](#).

Maximum daily dose (mg/kg/day)

Definition of maximum daily dose is in Section [5.1.2.4](#).

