5.6.2 Adverse Events

AEs will be tabulated by MedDRA system organ class (SOC) and MedDRA preferred term (PT). The number and percentage of participants experiencing each event at least once will be summarized. All summaries will be sorted alphabetically by SOC and by frequency of events within PTs, starting with the most frequent event overall.

AEs will be classified as ongoing at entry, treatment-emergent and post-treatment. Ongoing AEs at entry are defined as AEs which had an onset date prior to the first EP0151 dose of LCM.

TEAEs will be defined as those events which started on or after the date of first dose of LCM in EP0151, or events for which severity worsened on or after the date of first dose of LCM in EP0151. AEs which occur within 30 days after final dose of LCM in EP0151 will be considered treatment-emergent. Post-treatment AEs are defined as AEs which had an onset date after 30 days after the last dose of LCM.

All AEs reported during the study including ongoing AE at entry and post-treatment AEs will be provided in a participant data listing. Ongoing AEs from EP0034 and SP848 will be followed up and reported in this study.

An overview of the incidence of TEAEs will provide the overall summary of TEAEs and the numbers and percentages of participants with at least 1 TEAE, with a serious TEAE, with a drug-related TEAE, with a severe TEAE. The number and percentage of participant discontinuations due to TEAEs, the number and percentage of all deaths (if applicable), and the number and percentage of participants with TEAEs leading to death (if applicable) will also be summarized.

The number and percentage of participants who discontinued due to SAE (regardless of treatment emergent) will also be summarized.

The following summaries of AEs will be provided by MedDRA primary SOC and PT:

- Incidence of TEAEs
- Incidence of serious TEAEs
- Incidence of non-serious TEAEs
- Incidence of ongoing AEs at EP0151 study entry
- Incidence of TEAEs leading to discontinuation
- Incidence of SAEs leading to discontinuation
- Incidence of TEAEs related to potential drug-induced liver injury (PDILI) (defined in

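### SAEs that are neither treatment-emergent nor a cause of discontinuation enter no SAE-specific table in the SAP, although Protocol 9.3.1 plans an unrestricted SAE table and SAP 6.2 declares no change

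*SAP*

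**What the plan says.** Protocol 9.3.1 lists the event groups to be tabulated, and the list ends with "withdrawals due to SAEs, and SAEs will be tabulated by system organ class and preferred term". Earlier in the same sentence the treatment-emergent qualifier is attached to several groups (TEAEs, non-serious TEAEs, withdrawals due to TEAEs). It is not attached to SAEs.

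SAP 5.6.2 gives the tables by SOC and PT. Two concern serious events as a group: "Incidence of serious TEAEs" and "Incidence of SAEs leading to discontinuation". The overview table counts participants with a serious TEAE. For withdrawals the SAP drops the restriction: "The number and percentage of participants who discontinued due to SAE (regardless of treatment emergent) will also be summarized". SAP 5.3.1 defines the matching primary endpoint by the seriousness flag alone: "The premature study termination due to AE collected in eCRF will be further considered for AEs indicated as serious in the eCRF".

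Two classes of AE can fall outside the TEAE definition. The first is AEs ongoing at entry: "Ongoing AEs at entry are defined as AEs which had an onset date prior to the first EP0151 dose of LCM"; they count as TEAEs only if their severity worsens on or after the first EP0151 dose. The second is post-treatment AEs, with onset more than 30 days after the last dose. All AEs, in both classes, go into a participant listing.

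Protocol 8.3.1 asks sites to collect SAEs "up to 30 days from the end of the study for each study participant", and SAEs that may be drug-related without a time limit. SAP 6.2 reports no departure from the analyses planned in the protocol.

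**The concern.** The protocol promises a table and the SAP supplies a narrower one without saying so. In a single-arm descriptive study with no hypothesis test, the safety tables are the main result, so a reader will take the serious-event table as the full SAE count. If an SAE is collected but falls outside the TEAE definition, that count is lower than the one the protocol describes, and the table gives no sign of it.

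The SAP also uses two event sets for serious events: treatment-emergent only in the general table, and any SAE in the discontinuation table. A reader who compares the two could find an SAE in the second that is missing from the first, with no stated reason.

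**Working it through.** No sample size, power or event-rate figure is involved. The check is a comparison of text plus a short calculation of the collection window.

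**1. Planned against specified**

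| Event group | Protocol 9.3.1 | SAP 5.6.2 |
|---|---|---|
| SAEs, general table by SOC and PT | SAEs, unrestricted | Serious TEAEs only |
| SAEs causing withdrawal, by SOC and PT | Withdrawals due to SAEs | SAEs leading to discontinuation, unrestricted |
| All AEs | Listed | Listed |

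Only the first row differs. The protocol sentence uses the treatment-emergent qualifier for other groups, and the SAP separates the two ideas when it counts SAE discontinuations. So SAEs in the protocol is not plainly shorthand for serious TEAEs.

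**2. Post-treatment SAEs in a child who tapers**

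Inputs: the Final Visit is 30 days (-1/+3) after the final dose (Protocol Table 1-1 footnotes); SAE collection runs 30 days beyond the child's end of study (Protocol 8.3.1); the TEAE window closes 30 days after the last dose (SAP 5.6.2). Assumption: the child's end of study is the last visit.

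- Final Visit: day 30 - 1 = 29 to day 30 + 3 = 33.
- End of SAE collection: 29 + 30 = day 59 to 33 + 30 = day 63.
- Collected but not treatment-emergent: from day 31, lasting 59 - 30 = 29 to 63 - 30 = 33 days.

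**3. Post-treatment SAEs in a child who moves to prescribed lacosamide**

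The Termination Visit is the last visit (Protocol 4.1). If the last study dose is taken at that visit, collection ends about day 30, when the TEAE window also closes. Almost no gap remains.

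**4. AEs ongoing at entry that become serious**

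Exclusion criterion 4 bars an ongoing SAE but not an ongoing non-serious AE, and SAP 5.6.2 carries ongoing parent-study AEs into EP0151. The TEAE rule looks at onset and worsened severity. Protocol Appendix 3 treats severity and seriousness as separate ratings. An ongoing event that becomes serious with no change in intensity is therefore not a TEAE. It would appear in the table of AEs ongoing at entry, which is not split by seriousness.

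**5. Size per case**

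One child in 100 is 1/100 = 1.0%; one in 80 is 1/80 = 1.25%. The documents give no expected number of such children.

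**The case against.** The strongest reply is that very little is lost. Each part is taken in turn.

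- **Withdrawals are covered.** A reader might infer that an SAE can count in the primary endpoint "Withdrawals from study due to SAEs" and yet be missing from every SAE table. The documents do not support that. Such an event appears in the SOC and PT table of SAEs leading to discontinuation, in its repeat with site and participant numbers, and in the unrestricted discontinuation count. It can be absent only from the serious-TEAE table. An SAE starting more than 30 days after the last dose will also rarely be a reason for premature termination. This part of the reply stands.
- **The ongoing-at-entry class is very small.** Exclusion criterion 4 removes ongoing SAEs. Protocol 8.3.1 requires AEs that recur or worsen after Visit 1 to be reported, and Appendix 3 makes an exacerbation in frequency or intensity an AE. Most events that lead to hospitalisation would then be recorded as new or worsened, and so count as TEAEs. This also stands.
- **The window is short.** A reader might infer that about half of SAE follow-up goes untabulated. That describes only the post-dose window of about 60 days, and only for children who taper. Against whole follow-up, assuming a 28-day taper, the share is 30/(205 × 7 + 28 + 60) = 30/1523, about 2%, after 205 weeks of treatment, and 30/(52 × 7 + 28 + 60) = 30/452, about 7%, after 52 weeks. Post-treatment SAEs are also less informative about the drug.
- **Nothing is hidden.** All AEs are listed and all deaths are counted. This is correct, but a listing does not meet a commitment to tabulate, and the statement in SAP 6.2 remains inaccurate on this point.

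**Conclusion.** The mismatch is real and narrow. Protocol 9.3.1 plans an SAE table without a treatment-emergent limit, SAP 5.6.2 restricts the general table to serious TEAEs, and SAP 6.2 does not declare it. SAEs that are not treatment-emergent and do not lead to discontinuation enter no SAE-specific incidence table.

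The events at issue are mainly those with onset from day 31 to about day 59 to 63 after the last dose in children who taper. This rests on reading each child's end of study as the last visit. For children who continue on prescribed lacosamide the gap nearly vanishes, if their last study dose falls at the Termination Visit. Whether any SAE is actually omitted depends on one occurring in these classes. The number is probably small and cannot be derived from the documents; each affected child would move the incidence by 1.0 to 1.25 percentage points.

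The documents do not support the inference that the SAE-withdrawal endpoint is miscounted or that SAEs are concealed. The point is completeness of the SAE table and agreement between protocol and SAP, and it should be corrected before the SAP is final.

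**What to change.** Add to SAP 5.6.2 a table of the incidence of all SAEs, regardless of treatment emergence, by SOC and PT. Keep the serious-TEAE table as a subset of it. Columns for ongoing at entry, treatment-emergent and post-treatment would help a reader reconcile the two tables but are optional.

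If the sponsor prefers the restriction, the minimum is to state and justify it in SAP 6.2. That corrects the declaration but does not deliver the table the protocol describes.

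The cost is one extra table from SAE data that the protocol already requires. One check is needed: Protocol Appendix 3 lets sites report SAEs on paper or by telephone once the electronic tool is off-line, so the sponsor should confirm that late SAEs reach the analysis database.

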Appendix 6.1.7)

- Incidence of TEAEs by relationship to LCM
- Incidence of fatal TEAEs by relationship to LCM
- Incidence of non-serious TEAEs by relationship to LCM
- Incidence of non-serious TEAEs occurring in at least 5% of participants
- Incidence of TEAEs by maximum intensity
- Incidence of other significant TEAEs (defined in Appendix 6.1.6)
- Incidence of drug-related TEAEs by seriousness
- Incidence of TEAEs by 100 participant-months of exposure. The event rates are derived using the total number of TEAEs, including unique and non-unique TEAEs, divided by the participant-months exposed, and multiplied by 100.

In addition, summaries for the incidence of TEAEs overall, incidence of serious TEAEs, incidence of TEAEs leading to discontinuation, incidence of SAEs leading to discontinuation, TEAEs related to PDILI, other significant TEAEs, and pediatric growth-, neurodevelopment-, behavior-, and endocrine-related TEAEs will be repeated presenting the site and participant number of all those participants experiencing each TEAE as well as in participant data listings. Pediatric growth-, neurodevelopment-, behavior-, and endocrine-related TEAEs will be determined by manual medical review of reported MedDRA PTs.

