### Early Termination Visit with tapering of LCM

Study participants who discontinue prematurely from EP0151 and who will not continue further treatment with LCM should gradually taper LCM. These study participants will perform an Early Termination Visit followed by the visits required for the End of Study Period. Study participants should be tapered off LCM at the recommended decrements (Table 6-2). The Taper Period is up to 4 weeks; a slower taper or faster taper is permitted, if medically necessary; however, the maximum duration of tapering should not exceed 6 weeks. All study participants who taper off LCM will attend a Final Visit 30 days after the final dose of LCM. In the case of LCM withdrawal and taper, the Investigator is allowed to add any other antiepileptic drugs (AEDs) during the End of Study Period, following the Investigator's medical judgment.

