5.1.2 General study level definitions

5.1.2.1 Analysis Time Points

5.1.2.1.1 First and last dose of LCM

Unless otherwise noted, all references to the first dose of LCM in this SAP refer to the first dose of LCM during EP0151 (ie, not the first dose of LCM from the previous study in which participants participated prior to EP0151). Unless otherwise noted, all references to the last dose of LCM in this SAP refer to the last dose of LCM in EP0151.

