5.1.2.3 Exposure duration

The overall duration of LCM exposure for each participant will be calculated as the date of the last dose of LCM minus the date of the first dose of LCM plus 1 day. Gaps in treatment or days with unknown dosing will not be subtracted from the duration of exposure. The duration of LCM exposure will be summarized descriptively, separately, as a continuous parameter (in days) and as a categorical parameter, where categories will be defined using the following cumulative 6-month intervals for the Treatment Period: >0 months, >6 months, >12 months, >18 months, >24 months, >30 months, >36 months, >42 months, and >48 months, where 1 month is defined as 28 days.

Participant-years of LCM exposure in the study is calculated as the duration of exposure (days) divided by 365.25.

Participant-years of LCM exposure will be summarized using the following cumulative 6-month time intervals for the Treatment Period: >0 months, >6 months, >12 months, >18 months, >24 months, >30 months, >36 months, >42 months, and >48 months.

Participant-months of exposure will be calculated as the sum of days of exposure divided by 28.

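### The TEAE rate per 100 participant-months counts events up to 30 days after the last dose but divides by time that ends at the last dose, so it is biased upward, probably by a few percent or less

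*SAP*

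**What the plan says.** The rate is the last item in the list of adverse event summaries in SAP 5.6.2. It takes every TEAE, repeats included, "divided by the participant-months exposed, and multiplied by 100".

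- **Numerator.** SAP 5.6.2 states that "AEs which occur within 30 days after final dose of LCM in EP0151 will be considered treatment-emergent". Protocol 9.3.1 has the same window. Nothing limits the numerator of this rate to on-treatment onset.
- **Denominator.** SAP 5.1.2.3 defines exposure for each child as the "date of the last dose of LCM minus the date of the first dose of LCM plus 1 day", and then: "Participant-months of exposure will be calculated as the sum of days of exposure divided by 28". No post-dose days are added. SAP 5.1.2.1.1 adds that "all references to the last dose of LCM in this SAP refer to the last dose of LCM in EP0151". I read this as including taper doses, so taper time is already in the denominator and only the 30 days are unmatched.
- **Gaps.** SAP 5.1.2.3 also says: "Gaps in treatment or days with unknown dosing will not be subtracted from the duration of exposure".
- **Who is observed after the last dose.** Protocol 4.1 says: "All study participants who taper off LCM will attend a Final Visit 30 days after the final dose of LCM". Under the same section, children who move to prescribed lacosamide have the Termination Visit as their last visit. For them, Protocol 8.3.1 continues only the collection of serious adverse events (SAEs), for 30 days after each participant's end of study.
- **Presentation.** SAP 5.1 presents summaries overall and by age at entry (2 to under 4 years, 4 to under 6 years) unless stated otherwise.

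**The concern.** An event rate needs events and time drawn from the same window. Here the event window runs 30 days past the time window. The mismatch is also uneven: a child who tapers off is seen for the 30 days, while a child who moves to prescribed lacosamide contributes at most SAEs in that time.

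TEAEs are a primary endpoint. The other adverse event summaries listed in SAP 5.6.2 are participant counts and percentages, which take no account of follow-up that can run to about 205 weeks. This rate is the one summary in that list that does, so it is the one a reader would use to set one age group beside the other. Treatment normally ends at age 6, or earlier on regional approval (Protocol 4.1, Termination Visit), so older entrants have shorter maximum exposure. The same 30 days then weigh more heavily in their rate.

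**Working it through.** **Stated figure.** The documents give no TEAE rate or expected event count, so there is none to reproduce. The maximum duration is consistent with the 30 days falling after treatment and taper: 205 + 4 + 30/7 = 213.3 weeks, against a stated 213.

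**Inputs from the documents.** Window after last dose: 30 days (SAP 5.6.2). Month: 28 days (SAP 5.1.2.3). Maximum Treatment Period: 205 weeks = 1435 days (SAP 1.2). Visit spacing: 26 weeks = 182 days (SAP 1.2). Participants: 80 to 100 (SAP 3).

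**Assumed inputs.** The share f observed through the window, the mean exposure D in days, and r, the post-dose event rate divided by the on-treatment rate.

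**Formulas.**
- Against a time-at-risk rate, the events are the same and only the denominators differ. The ratio is (D + 30f)/D, so the excess is 30f/D whatever the value of r.
- Against an on-treatment rate (events through last dose only), the excess is 30fr/D. The two agree when r = 1.

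**Pooled excess, 30f/D.**

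| Mean exposure | f = 10% | f = 25% | f = 50% | f = 100% |
|---|---|---|---|---|
| 52 weeks (364 days) | 0.8% | 2.1% | 4.1% | 8.2% |
| 104 weeks (728 days) | 0.4% | 1.0% | 2.1% | 4.1% |
| 205 weeks (1435 days) | 0.2% | 0.5% | 1.0% | 2.1% |

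Against an on-treatment rate, these are halved at r = 0.5 and doubled at r = 2. At 104 weeks and f = 25%, for example, the excess is 0.5%, 1.0% and 2.1% for r = 0.5, 1 and 2.

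**Worked example (all inputs assumed).** True rate 20 per 100 participant-months, r = 1, N = 100. Twenty children stop at 26 weeks and taper, 10 finish at 104 weeks and taper, and 70 finish at 104 weeks and move to prescribed lacosamide.
- Exposure: 20 x 182 + 80 x 728 = 61,880 days = 2210 participant-months.
- Unmatched time: 30 x 30 = 900 days.
- Expected events: (0.20/28) x 62,780 = 448.4.
- SAP rate: 100 x 448.4/2210 = 20.29.
- Matched rate: 100 x 448.4/(62,780/28) = 20.00.
- Excess: 900/61,880 = 1.5%. With N = 80 and the same proportions the result is identical.

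**Age groups (illustration).** Suppose mean exposure is 52 weeks in the older group and 156 weeks (1092 days) in the younger. At f = 100% in both, the excesses are 30/364 = 8.2% and 30/1092 = 2.7%, about 5.5 points apart. At f = 10% in both they are 0.8% and 0.3%, about half a point apart.

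**The case against.** The strongest case against acting is that the table is labelled as events per participant-months of exposure. It reports TEAEs, as the protocol defines them, per unit of drug exposure. The protocol does not list this rate, no hypothesis is tested, and the excess is small. Treatment gaps counted as exposure push the rate down and could offset part of the excess relative to true on-drug time. All of this stands and limits the severity. It does not remove the mismatch, because no text aligns the two windows and a reader of the table would not know of it.

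Four stronger readings are tempting, and the documents do not support them.

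- **A large bias for early stoppers.** For one child followed for the full 30 days, the ratio is 30/182 = 16.5% at 26 weeks and 30/1435 = 2.1% at 205 weeks. These are per-child figures. The planned output is pooled and by two age groups, and no rate is planned for children who stop early.
- **Every child who stops contributes 30 extra days.** Footnote d of Protocol Table 1-1 links the End of Study Period and Final Visit to children who require taper, and Protocol 6.1 links taper to a dose of 3 mg/kg/day or higher. So f may be well below 100%.
- **Withdrawal-related events make the excess larger.** This is true only against an on-treatment rate (r above 1). Against a time-at-risk rate the excess does not depend on r.
- **Comparison with EP0034 and SP848 is distorted.** No such comparison is specified, and these documents do not give the parent studies' rate definition.

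**Conclusion.** The mismatch follows from the SAP's own definitions, and its direction is certain: it raises the rate, or leaves it unchanged if no event falls in the window or no child is observed there. Its size is modest. Under the assumed ranges the pooled excess runs from 0.2% to 8.2%, and a few percent or less is the likely result, because long exposures dominate the denominator and children on prescribed lacosamide add few post-dose events. The main way it could mislead is between the two age groups, where exposure differs by design.

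The figures rest on assumed values of f and mean exposure, on r = 1 where the comparison is with an on-treatment rate, and on reading the last dose as including taper doses. Participant counts and percentages are not affected, and there is no error rate to affect. Severity: minor.

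**What to change.** In SAP 5.6.2, for this rate only, choose one of two options.

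1. **On-treatment numerator (simpler).** Count only TEAEs with onset or worsening from the first through the last lacosamide dose in EP0151. Keep participant-months as defined in SAP 5.1.2.3. Use the same last-dose date in numerator and denominator, including where SAP 5.1.1.4 imputes it for exposure duration.
2. **Time-at-risk denominator.** Run it from first dose to the earliest of last dose + 30 days, last contact or death, ending at the Termination Visit for children who move to prescribed lacosamide. Exclude from this rate's numerator any event after that end date, including SAEs collected after the Termination Visit under Protocol 8.3.1. Without that exclusion the mismatch persists for those children.

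Leave all other TEAE tables and the exposure tables unchanged.

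The cost is a sentence or two in the SAP, one derived variable from dates the SAP already uses, and a footnote. Under option 1 the footnote says that this rate omits post-dose TEAEs shown in the other tables. Under option 2 it says that the denominator differs slightly from the exposure table and that events after the end date are left out.
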